#### 5.15.1 Modification of Study Treatment

At the discretion of the local investigator, immunosuppression protocols may be modified or discontinued if there are signs of reactions to any of the medications or if there is a serious infection.

#### 5.15.2 Modification of Standard Immunosuppression

#### 5.15.2.1 RABBIT ANTI-THYMOCYTE GLOBULIN-INDUCED ANAPHYLAXIS

In rare instances, anaphylaxis has been reported with Thymoglobulin® use. In such cases, the infusion should be terminated immediately. Medical personnel should be available to treat subjects who experience anaphylaxis. Emergency treatment such as 0.3 mL to 0.5 mL aqueous epinephrine (1:1000 dilution) subcutaneously and other resuscitative measures including oxygen, IV fluids, antihistamines, corticosteroids, pressor amines, and airway management, as clinically indicated, should be provided. Thymoglobulin® or other rabbit immunoglobulins should not be administered again for such subjects.

#### 5.15.2.2 RABBIT ANTI-THYMOCYTE GLOBULIN-INDUCED CYTOKINE RELEASE

Thymoglobulin® infusion may cause cytokine release-related fever and chills. To minimize these, the first dose should be infused over a minimum of 6 hours into a high-flow vein. Also, premedication with corticosteroids, acetaminophen, and/or an antihistamine will be provided in order to minimize the reaction incidence and/or intensity. At any sign of the above reaction, slowing the infusion rate by 50% will also occur.

#### 5.15.2.3 NEUTROPENIA

Neutropenia is an expected consequence of the administration of several medications in this protocol. Subject safety is of utmost importance. Clinical treatment decisions take precedence over recommended guidelines.

# If a subject's absolute neutrophil count is less than 1000 cells/ $\mu$ L and the subject is afebrile, then the following will be done:

- Reduce rabbit ATG by 50%.
- Reduce the prophylactic use of valganciclovir from 900 mg per day to 450 mg per day or hold valganciclovir.
- Reduce trimethoprim/sulfamethoxazole to 80/400 mg on Monday, Wednesday, and Friday or hold trimethoprim/sulfamethoxazole.
- Review and obtain current sirolimus trough levels and consider dosage adjustment if trough level are >12ng/mL.
- If subject is using mycophenolate mofetil or mycophenolate sodium in lieu of sirolimus, consider dose reduction.
- Consider administration of G-CSF.
- Monitor temperature BID.
- Follow up within 48-72 hours to obtain: repeat complete blood count (CBC) with differential, subject symptoms, and measured temperatures.

# If a subject's absolute neutrophil count is less than 1000 cells/ $\mu$ L and the subject is febrile, then the following will be done:

- Obtain Infectious Disease Consult.
- Hold rabbit ATG.
- Hold valganciclovir and trimethoprim/sulfamethoxazole.
- Review and obtain current sirolimus trough levels and consider dosage adjustment if trough level are >12ng/mL.
- If subject is using mycophenolate mofetil or mycophenolate sodium in lieu of sirolimus, consider dose reduction.
- Administer G-CSF.
- Monitor temperature BID.
- Follow up within 48-72 hours to obtain: repeat CBC with differential, subject symptoms, and measured temperatures.

# If a subject's absolute neutrophil count is measured as less than 500 cells/ $\mu$ L and the subject is afebrile, then the following will be done:

- Hold rabbit ATG.
- Hold administration of trimethoprim/sulfamethoxazole and/or valganciclovir.
- Review and obtain current sirolimus trough levels and hold dose if trough level are >12ng/mL.
- If subject is using mycophenolate mofetil or mycophenolate sodium in lieu of sirolimus, consider holding dose.
- Obtain CMV antigenemia or PCR for CMV.
- Consider fluoroquinolones in afebrile subjects.
- Consider clotrimazole.
- Administer G-CSF.
- Monitor temperature BID.

- Clinical Islet Transplantation C Protocol CIT-01
  - Follow up within 24 hours to obtain repeat CBC, subject symptoms, and measured temperatures.

# If a subject's absolute neutrophil count is measured as less than 500 cells/ $\mu$ L and the subject is febrile, then the following will be done:

- The subject will be hospitalized under neutropenic precautions and Infectious Disease/Hematology consult will be obtained.
- Hold rabbit ATG.
- Hold administration of trimethoprim/sulfamethoxazole and/or valganciclovir.
- Review and obtain current sirolimus trough levels and hold dose if trough level are >12ng/mL.
- If subject is using mycophenolate mofetil or mycophenolate sodium in lieu of sirolimus, consider holding dose.
- Obtain CMV antigenemia or PCR for CMV.
- Administer G-CSF.

## 5.15.2.2 THROMBOCYTOPENIA

If the subject is found to have a platelet count (PLT) of  $<50 \times 10^{9}$ /L, ATG will be withheld until PLT  $>50 \times 10^{9}$ /L, then resume at a 50% reduced dose. *If the PLT is between 50 and 75 x 10^9*/L, *reduce anti-thymoglobulin dose by 50% until PLT is >75 x 10^9*/L.

If the PLT is  $<50 \times 10^{9}/L$ , sirolimus will be withheld for 24 hours, then resumed at a 50% reduced dose. If PLT fails to return to  $>50 \times 10^{9}/L$  within one week, sirolimus is to be withheld until PLT  $>50 \times 10^{9}/L$ , after which sirolimus is resumed at 50% of the dose that preceded the drop in PLT to  $<50 \times 10^{9}/L$ .

## 5.15.2.3NEPHROTOXICITY

An increase in serum creatinine (sustained 33%), warrants an evaluation with the institutions nephrologist. Evaluation should at least include GFR, urinary culture, tests for albuminuria, red/white blood cells in urine and an ultrasound. Possible harmful effects of medication should also be evaluated. If the lowering of function is thought to be attributable to the treatment with calcineurin inhibitor the trough level of this compound should be lowered to the lower limit of the span given in section 5.7. If this is not enough and other causes are ruled out the patient can be switched from Prograf/Sandimmune to Sirolimus. Renal function should be reevaluated within 3 months.

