### 1.5.2.1 RABBIT ANTITHYMOCYTE GLOBULIN (THYMOGLOBULIN®)

Rabbit Thymoglobulin® was approved by the FDA in 1999 for the treatment for acute renal graft rejection in conjunction with concomitant immunosuppression (see product monograph for details). It is a polyclonal IgG antibody obtained by immunization of rabbit with human thymocytes and contains cytotoxic antibodies directed against antigens expressed on human T lymphocytes. Thymoglobulin® has shown a consistent safety profile with most AEs being manageable and reversible; the most common events are fever, chills and leukopenia. While rare, the most severe events include allergic or anaphylactoid reactions and serum sickness. As with all immunosuppression, administration of Thymoglobulin® may be associated with an increased risk of infection and development of malignancy (especially of the skin and lymphoid system).

In 82 kidney transplant recipients receiving 1.5 mg/kg/day for 7 – 14 days, the principal AEs were fever (52%) and chills (47%) associated with the infusions, leucopenia (47%), and thrombocytopenia (30%). CMV infection (13%) and PTLD (2%). Neutropenia has been described; anaphylaxis has been reported rarely.

Published results of the use of Thymoglobulin® in clinical and experimental islet transplantation are limited to relative small cohorts. Hirshberg *et al.* described the successful role of rabbit ATG and sirolimus in reducing rejection of islet allografts in primates, with no evidence of direct islet toxicity from Thymoglobulin®(Hirshberg, Preston et al. 2003). Hering *et al.* described a beneficial role of Thymoglobulin® induction (6mg/kg) in 8 patients with T1D receiving single donor islet grafts, all of whom achieved insulin independence and were protected against recurrence of

hypoglycemia(Hering, Kandaswamy et al. 2005). Acute islet rejection was described in patients receiving calcineurin-free immunosuppression when sirolimus levels fell below 9ng/mL. The use of higher doses of sirolimus exacerbated the neutropenic side effects of Thymoglobulin®, but these could be managed safely without risk of opportunistic infections when appropriate dose reduction and/or administration of

Granulocyte Colony Stimulating Factor (G-CSF; Neupogen®) if required[12]. Studies comparing risk profiles between Thymoglobulin® and Basiliximab® have shown relatively small differences

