## 5.7 Cell Proliferation Inhibitor

All subjects will receive one of the following cell proliferation inhibitors (MMF OR Sirolimus):

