#### 5.7.2 Rapamune® (Sirolimus)

Sirolimus therapy will be administered orally, either as liquid or tablets., The sirolimus will be administered pre-transplant at a loading dose of 0.05-0.2 mg/kg BW, followed by the same dose days 1-2 and with 0.1 mg/kg once daily from day 2-3.

Doses are adjusted to achieve whole-blood trough levels:

Time Point	
Day 7-90	10 –15 ng/mL
> 3 months	7-10 ng/mL

Sirolimus dose may be adjusted for side effects listed in the SPC provided by EMEA product monographs (www.emea.eu.int); such leukopenia, thrombocytopenia, anemia, GI toxicity and opportunistic infections.

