#### 5.8.1 Prograf® (Tacrolimus)

Tacrolimus is the preferred calcineurin inhibitor for this study. Tacrolimus will be administered orally; beginning the day after the first transplantation and continued throughout the study. Doses are adjusted to achieve whole-blood trough levels:

First, second and thirdTransplantation:

Time Point	
Day 1-90	10-12 ng/mL
Month 3-6	8-10 ng/ml
Month >6	6-8 ng/ml

If Sirolimus is used Tacrolimus levels may be reduced by 20%.

Tacrolimus dose may be adjusted for side effects listed in the SPC provided by EMEA product monographs (www.emea.eu.int); such as nephrotoxicity, neurotoxicity, GI toxicity and opportunistic infections.

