## 5.13 Rescue Medications

Rescue therapy will not be initiated in this protocol to treat suspected rejection. Immunologic surveillance methods that would allow diagnosis of islet allograft rejection early enough for timely intervention have yet to be identified and validated.

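### The nephrotoxicity rule sends sites to section 5.7 for the calcineurin inhibitor trough, but 5.7 tabulates only sirolimus; the calcineurin inhibitor spans are in 5.8

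*Protocol*

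**What the plan says.** The nephrotoxicity rule (Protocol 5.15.2.3, the second subsection with that number) starts from a sustained 33% rise in serum creatinine and calls for a work-up. Where the calcineurin inhibitor is held responsible, the rule is that the trough of that drug "should be lowered to the lower limit of the span given in section 5.7". If that is not enough and other causes are excluded, "the patient can be switched from Prograf/Sandimmune to Sirolimus".

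Section 5.7 is headed Cell Proliferation Inhibitor and opens with "All subjects will receive one of the following cell proliferation inhibitors (MMF OR Sirolimus". Its only trough table, in 5.7.2, is for sirolimus. The tacrolimus spans are in 5.8.1 and the cyclosporine spans in 5.8.2. Table 1 in section 5.1 also places the calcineurin inhibitor under 5.8.

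Three further places bear on the same rule:
- Sections 1.4, 5.7 and 5.8 describe one proliferation inhibitor plus one calcineurin inhibitor. Tacrolimus is given "beginning the day after the first transplantation and continued throughout the study".
- Section 5.7.2 starts sirolimus with a pre-transplant loading dose of 0.05-0.2 mg/kg, "followed by the same dose days 1-2 and with 0.1 mg/kg once daily from day 2-3".
- Section 1.5.2.1, background on anti-thymocyte globulin, states: "Acute islet rejection was described in patients receiving calcineurin-free immunosuppression when sirolimus levels fell below 9ng/mL".

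**The concern.** This is an operative safety rule for a foreseeable event: section 1.5.2.5 lists nephrotoxicity as a tacrolimus side effect, and reduction in GFR is among the safety endpoints in 4.1.4. A site that looks up the cited section finds a table for another drug. The tacrolimus and sirolimus spans are both in ng/mL and of similar size, so the wrong number would look plausible.

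The step after that, the switch to sirolimus, does not say what the resulting combination is. A subject on MMF would then take two proliferation inhibitors; a subject already on sirolimus would be left with sirolimus alone. Neither case is addressed. The sirolimus section to which such a subject would turn has a loose starting rule and gives no separate range for use without a calcineurin inhibitor.

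What is at stake is mainly consistent handling of a safety event across seven centers.

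**Working it through.** No sample-size, power or alpha figure bears on this point, so the check sets the tables side by side.

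**1. Lower trough limits (ng/mL), from the tables in 5.7.2, 5.8.1 and 5.8.2**

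| Period | Sirolimus (5.7.2), the literal reading | Tacrolimus (5.8.1) | Cyclosporine (5.8.2) |
|---|---|---|---|
| to day 90 | 10 (table starts at day 7) | 10 | 200 |
| months 3-6 | 7 | 8 | 150 |
| after month 6 | 7 | 6 | 100 |

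Tacrolimus, literal minus tabulated floor: 10 - 10 = 0; 7 - 8 = -1; 7 - 6 = +1 ng/mL.

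Cyclosporine, tabulated floor divided by literal: 200/10 = 20; 150/7 = 21.4; 100/7 = 14.3. The literal figure is not usable as a cyclosporine floor.

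The tacrolimus comparison uses the tabulated spans. Section 5.8.1 allows a 20% reduction when sirolimus is used. If that applies to the floor, it becomes 0.8 x 10 = 8, 0.8 x 8 = 6.4 and 0.8 x 6 = 4.8, and the literal reading is then higher in every period.

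**2. The switch.** Default regimen: one proliferation inhibitor plus one calcineurin inhibitor. Replacing the calcineurin inhibitor by sirolimus gives:
- subject on MMF: MMF plus sirolimus;
- subject on sirolimus: sirolimus only, so there is no drug to switch to.

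**3. Day 2 of sirolimus.** The repeat of the loading dose covers days 1-2, and 0.1 mg/kg starts from day 2-3, so day 2 falls under both. If both were applied to day 2, the two figures could differ up to two-fold in either direction: 0.2/0.1 = 2 and 0.1/0.05 = 2.

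**4. Sirolimus ranges against the 9 ng/mL background report.** Share of a range below 9 = (min(upper, 9) - lower)/(upper - lower), not less than 0.
- Day 7-90, 10-15 ng/mL: 0%.
- After 3 months, 7-10 ng/mL: (9 - 7)/(10 - 7) = 67%.

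This is a share of the width of a target range. It is not a share of subjects or of time.

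**The case against.** **The slip corrects itself.** The sentence names the calcineurin inhibitor, the next section is headed with that class, and Table 1 lists it under 5.8. A reader might infer that sites would steer cyclosporine to 7-10 ng/mL; that would mean applying a table labelled sirolimus to a drug with limits 14 to 21 times higher, and it is unlikely. This argument stands for cyclosporine. It is weaker for tacrolimus, where the wrong figure is plausible, and it does not make the cited section right.

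**The switch is allowed.** A reader might infer that it contradicts the regimen. Section 1.4 says treatment is to be adapted to tolerability and that changing between the listed agents for clinical reasons is not a deviation. Section 5.15 lets the site investigator prescribe an alternative when the regimen is not tolerated, and 5.15.1 allows modification. The switch is thus a permitted, conditional exception. That settles whether it is a deviation; it does not say which combination follows, and the subject already on sirolimus remains uncovered.

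**The 9 ng/mL figure.** A reader might infer that the protocol directs subjects to levels it associates with rejection, the more so because "Rescue therapy will not be initiated in this protocol to treat suspected rejection". The documents do not support this. The figure is background from a cited series, and the protocol does not adopt it as a threshold. Section 1.5.2.1 does not say what else those patients took. The nephrotoxicity rule names no sirolimus target after the switch; 5.7.2 is inferred because it is the only one given. The day 7-90 range lies wholly above 9. What remains is a question for the clinicians.

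**Day 2.** The wording can be read as a flexible handover on day 2 or day 3, and doses are later adjusted to trough. The text does not say so, and the point is separate from nephrotoxicity.

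**Effect on results.** With 18 subjects per arm, one graft loss moves a day-365 proportion by 1/18 = 5.6 percentage points, so a reader might infer damage to those endpoints. That is speculative: the number of subjects reaching this rule is unknown, and both arms follow the same rule, so no bias between arms is shown.

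**Conclusion.** The cross-reference is wrong, and this follows from the section headings and tables alone. Its literal effect on the tabulated tacrolimus floor is 0 to day 90, -1 ng/mL in months 3-6 and +1 ng/mL after month 6; for cyclosporine the reference yields no usable floor. The primary endpoint at 75 ± 5 days falls where the tacrolimus and sirolimus floors coincide, so it is largely untouched.

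Two gaps in the same set of rules are real but smaller: the combination after a switch to sirolimus, chiefly for a subject already on it, and the overlapping day-2 instruction. The range after 3 months is a lesser point still. It rests on two assumptions, that 5.7.2 applies after the switch and that the background report is comparable, and neither is stated in the protocol.

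**What to change.** - Correct the reference in the nephrotoxicity rule of 5.15.2.3 so that it points to the calcineurin inhibitor spans in 5.8.
- In the same edit, have the sponsor's clinicians reconcile the switch to sirolimus with sections 1.4, 5.7 and 5.8: state which combination is meant, including for a subject already on sirolimus, and refer to the latitude that 1.4 already gives.
- Have them reconcile the two instructions in 5.7.2 that both cover day 2.
- As a lesser item, have them state whether the sirolimus range after 3 months is meant for subjects without a calcineurin inhibitor, in view of the report in 1.5.2.1.

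The clinicians set any values; none is proposed here. The cost is a wording amendment, with no change to sample size, visits or analysis.

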## 5.15.3 Premature Discontinuation of Study Treatment

Study treatment may be prematurely discontinued for any subject for any of the following reasons:1.

The subject is unwilling or unable to comply with the protocol.2. The investigator believes that the study treatment is no longer in the best interest of the subject.3. Graft Failure: Islet allograft failure will be defined as absence of insulin production by transplanted islets, as evidenced by absence of c-peptide <0.1nmol/L (<0.3 ng/mL). This will be determined by (1) c-peptide <0.1nmol/L (<0.3 ng/mL) on random testing, followed by (2) c-peptide<0.1nmol/L (<0.3 ng/mL) at baseline, and at 60 and 90 minutes after MMTT. C-peptide levels obtained in the course of the MMTT levels will be run at the core laboratory in Seattle, WA. Subjects with graft failure do not need to complete the day 75 metabolic assessments.

4. A unexpected related serious adverse event. The agent(s) to which the event is attributed will be discontinued.

Subjects who prematurely discontinue study treatment will remain in the study until normal termination, for the purpose of monitoring safety and efficacy parameters and will enter the reduced

schedule outlined in Appendix 2. Data from these subjects will be used in the intent-to-treat analysis. 6. Criteria for Premature Termination of the Study

## 6.1 Participant Withdrawal Criteria

Subjects who prematurely terminate from this study will not be replaced. Data from such subjects obtained before withdrawal of consent or before being lost to follow-up will be used in the intent-to-treat analysis. If a subject with functioning transplanted islets chooses to withdraw from the protocol, s/he must be informed of their risk for losing her/his islet graft and becoming sensitized if s/he chooses to discontinue immunosuppressive therapy and return to her/his original method of insulin management.

#### 6.1.1 Premature Termination from the Study

Subjects may be prematurely terminated from the study for the following reasons:

- 1. The subject elects to withdraw consent from all future study activities, including follow-up.
- 2. The subject is "lost to follow-up" (i.e., no further follow-up is possible because attempts to reestablish contact with the subject have failed).
- 3. The subject dies.

## 6.2 Study Stopping Rules

Study enrollment at all participating clinical sites will be suspended pending expedited review of all pertinent data by the institutional review board (IRB), the National Institute of Allergy and Infectious Disease (NIAID), the National Institute of Diabetes and Digestive and Kidney Diseases (NIDDK), and the NIDDK Data Safety Monitoring Board (DSMB), if any one of the following occurs:

- 1. The Medical Monitor finds any unexpected fatal or life-threatening adverse event possibly related to the use of the test therapy;
- 2. Primary non-function (PNF) occurs in 3 or more consecutive subjects at 2 or more participating clinical sites. PNF is defined as graft failure that occurs between 3-7 days post-transplant. Participants with graft failure do not need to complete the day 75 metabolic assessments.
- 3. There are 6 consecutive study subjects with a c-peptide less than 0.3 ng/mL (0.099nmol/L) (on random testing, at baseline and 1-3 hours post-MMTT) at 75 days post-transplant.
- 4. Any event(s) which in the opinion of the Medical Monitor or Protocol Chair indicates the need for DSMB review; or
- 5. The DSMB recommends termination of protocol enrollment and further transplants on a study-wide basis based on a review of the data and finding evidence that such action is necessary. Statistical guidelines for terminating the study based on monitoring guidelines are provided in section 10.

After the protocol is placed on hold, no additional transplants within the trial will be performed at any participating clinical site until the CIT Steering Committee and DSMB meet either in person or by conference call to review in depth the results and circumstances surrounding the islet functional failure or SAE to determine whether the trial enrollment of new subjects and conduct of additional transplants could be safely resumed.

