# **Study Definitions Page**

Control Arm- State of the Art	The study treatment group randomized to receive protocol specified immunosuppression without LMW-DS, including anticoagulative treatment with Heparin with the islet infusion.
Experimental Arm- Low Molecular Weight Sulfated Dextran	The study treatment group randomized to receive protocol specified immunosuppression with Low Molecular Weight Sulfated Dextran (LMW-DS), and excluding Heparin treatment.
Full Islet Graft Function	
 
Islet transplant recipients are considered to have full islet graft function if all of the following criteria are met: 
 
Titrated off insulin therapy for at least 1 week (7 consecutive days) with the last day within the day 75 and day 365 windows;
 
One HbA1c level, one fasting serum glucose level, and Mixed Meal Tolerance Test are documented within the visit window (e.g. 70-80 days at Day 75) and 7 consecutive days of blood sugar and insulin readings are documented within +/- 7 days of the visit window (e.g. 63-87 days at Day 75);
 
HbA1c <7.0% or a ≥2.5% decreased from baseline;
 
Fasting capillary glucose level should not exceed 140 mg/dL (7.8 mmol/L) more than three times in the 7 consecutive days (fasting is defined as 1st blood sugar reading of the day not noted as post-prandial or bedtime). Post-prandial capillary glucose level ≤ 126 mg/dL (≤7.0 mmol/L) at 90 minutes during the MMTT;
 
Fasting serum glucose level ≤ 126 mg/dL (≤7.0 mmol/L) from central lab results; if the fasting serum glucose level is > 126 mg/dL (>7.0 mmol/L), it must be confirmed in an additional one out of two measurements;
 
At least one MMTT fasting or stimulated c-peptide ≥0.5 ng/ml.
 
 
 

Graft Failure	Islet allograft failure will be defined as absence of insulin production by transplanted islets, as evidenced by absence of c-peptide <0.1nmol/L (<0.3 ng/mL). This will be determined by: (1) c-peptide <0.1nmol/L (<0.3 ng/mL) on random testing, followed by (2) c-peptide <0.1nmol/L (<0.3 ng/mL) at baseline, and at 60 and 90 minutes after MMTT. C-peptide levels obtained in the course of the MMTT levels will be run at the core laboratory in Seattle, WA. Subjects with graft failure do not need to complete the day 75 metabolic assessment.

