## 7.3 Randomization and Study Treatment Schedule

Once a compatible islet prep becomes available, then the site personnel will re-confirm the eligibility criteria. Eligible subjects will be randomized (1:1), to the experimental arm or control arm. A total of 36 subjects will be randomized; 18 subjects to an experimental arm and 18 subjects to a control arm.

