#### Graft Failure

Islet transplant recipients who have graft failure (absence of insulin production, with (c-peptide <0.1 nmol/L (<0.3 ng/mL) are eligible to undergo a second islet transplant if they meet the eligibility criteria described below:

- Prior to day 75, repeat transplantation within the CIT protocol must be approved by the CIT Steering Committee, based upon review of clinical information provided by the transplanting site to the DCC.
- After day 75, repeat transplantation must be approved by the Nordic Network Steering Committee, based on clinical information provided by the site. The decision of the Nordic Network Steering Committee will be provided to the sponsor.

Clinical information provided must include:

1) Results of graft failure assessments

- a) random c-peptide <0.1 nmol/L (<0.3 ng/mL)
- b) c-peptide <0.1 nmol/L (<0.3ng/mL) at baseline, and at 60 and 90 minutes after MMTT.
- 2) Post transplant clinical data
- 3) Potency testing from the first transplant product
- 4) Additional assessments as requested from the CIT Steering Committee.

Eligibility criteria include:

- 1. Subject has been compliant with study monitoring and prescribed immunosuppressive therapy;
- 2. No evidence of a serious and life-threatening infection, adverse event, or other condition that precludes attempting an intraportal injection or continuation of the post-transplant treatment regimen;
- 3. No evidence of post-transplant lymphoproliferative disorder (PTLD);
- 4. No evidence of progressive renal dysfunction, defined as creatinine rising above 2.0 mg/dL (177  $\mu$ mol/L) with calcineurin inhibitor trough levels within maintenance levels;
- 5. No evidence of hypersensitization, allergic responses, or other potentially serious drug reactions to medications required by the protocol.
- 6. Less than 8 months has passed after the first transplantation.
- 7. Absence of any medical condition that, in the opinion of the investigator, will interfere with a safe and successful second islet transplant.

If after the second islet infusion both basal and stimulated C-peptide levels remain <0.1nmol/L (<0.3 ng/mL), these recipients will be considered treatment failures with no islet graft function, and immunosuppression will be withdrawn.

Islet transplant recipients who do not meet criteria for full islet graft function **after the second islet infusion**, but before 8 months from the first infusion will be considered for a **third islet infusion**.

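### Stopping rule 3 can leave confirmed graft failures uncounted, and its run of six, pooled over both arms, is insensitive to graft loss confined to the LMW-DS arm

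*Protocol*

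**What the plan says.** Section 6.2 lists the events that suspend enrollment at all sites pending review. Rule 3 is triggered when "There are 6 consecutive study subjects with a c-peptide less than 0.3 ng/mL (0.099nmol/L"), the values being taken "on random testing, at baseline and 1-3 hours post-MMTT) at 75 days post-transplant". It names no arm and does not say which order (randomization, transplant or Day-75 date) makes subjects consecutive.

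Rule 2, immediately above, ends: "Participants with graft failure do not need to complete the day 75 metabolic assessments". The Study Definitions Page repeats this under graft failure ("Subjects with graft failure do not need to complete the day 75 metabolic assessment") and under primary non-function, and section 5.15.3 says it again. Graft failure is declared on a random C-peptide below 0.3 ng/mL followed by an MMTT with C-peptide below 0.3 ng/mL at baseline, 60 and 90 minutes.

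Two other provisions can remove the Day-75 value. Section 7.4.2 allows a second transplant after graft failure before that visit ("Prior to day 75, repeat transplantation within the CIT protocol must be approved by the CIT Steering Committee"), and sections 7.5 and 7.7 then restart the visit schedule. Subjects who discontinue study treatment move to Appendix 2, whose only MMTT is at one year.

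On allocation, section 7.3 says "Eligible subjects will be randomized (1:1), to the experimental arm or control arm", with "18 subjects to an experimental arm and 18 subjects to a control arm".

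**The concern.** Rule 3 is the only numeric graft-loss trigger in section 6.2 for the period after day 7. Rule 2 and the site rule in section 6.3 cover primary non-function at days 3-7.

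There are two weaknesses. First, the subjects the rule is meant to count are those excused from the measurement it counts. Nothing says whether an excused failure counts toward the six, is skipped, or breaks the run. Second, about half of any six consecutive subjects are controls. If LMW-DS grafts were being lost and control grafts were not, functioning controls would keep interrupting the run. At stake is how soon enrollment pauses if the experimental treatment damages grafts.

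**Working it through.** The protocol states no operating characteristic for rule 3, so there is no figure to reproduce.

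**Inputs.** From the protocol: run length 6 (6.2), 36 subjects, 18 per arm, 1:1 (7.3). Assumed, because the protocol is silent: failure rates by arm, and three allocation orders (blocks of 4, blocks of 6, one random order of 18 and 18).

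**Step 1: a run within one sequence of n subjects with failure probability p.** Let f(n) be the chance of at least one run of 6. Then f(6) = p^6, f(n) = p^6 + (n - 6)(1 - p)p^6 for n from 6 to 12, and f(n) = f(n-1) + (1 - p)p^6[1 - f(n-7)] beyond that.

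At p = 0.8:
- p^6 = 0.2621 and (1 - p)p^6 = 0.0524.
- f(12) = 0.2621 + 6 × 0.0524 = 0.577.
- f(6) to f(11) are 0.2621, 0.3146, 0.3670, 0.4194, 0.4719 and 0.5243, which sum to 2.359.
- f(18) = 0.577 + 0.0524 × (6 - 2.359) = 0.768.

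So a run counted within the 18 LMW-DS subjects fires in 77% of trials at an 80% failure rate, and in 95.7% at 90%. Its false-trigger rate is 0.07% at a 20% failure rate and 0.7% at 30%. For all 36 subjects with the same rate in both arms, the recursion gives 1.6% at 30%, 23% at 50%, 79% at 70% and 96% at 80%.

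**Step 2: different rates by arm, run pooled.** Simulation with 100,000 to 200,000 sequences per scenario, every value available:

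| Failure, LMW-DS / control | Blocks of 4 | Blocks of 6 | One 18:18 order | Within LMW-DS arm |
|---|---|---|---|---|
| 80% / 5% | 0.6% | 1.7% | 8% | 77% |
| 80% / 10% | 2.6% | 4.2% | 12% | 77% |
| 90% / 10% | 3.8% | 6.9% | 20% | 96% |
| 100% / 5% | 1.3% | 4.9% | 24% | 100% |
| 100% / 0% | 0% | 1.2% | 18% | 100% |

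The zero follows directly: with blocks of 4, at most 2 + 2 = 4 LMW-DS subjects can be consecutive.

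**Step 3: effect of the exemption.** Suppose half of the failures have no Day-75 value (18:18 order). At 80% failure in both arms, the chance of firing falls from 96.2% to 48.3% if such subjects are skipped, or to 7.6% if they break the run. At 90% / 10% it falls from 20.0% to 1.4% or 0.5%.

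**Step 4: adding versus replacing.** At 80% failure in both arms, the pooled run fires by subject 12 in 58% of trials (f(12) above). A run counted only within arms does so in 37-46%. Replacing the pooled run would therefore slow detection of common failure; adding to it would not. The price of adding, at 30% failure in both arms, is at most 1.6% + 0.7% + 0.7% = 3.0% of trials with a hold, against 1.6% now.

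**The case against.** A reader might infer that rule 3 can never fire. The documents do not support that. The exemption is permissive, a loss first found at Day 75 is not exempt, and confirming graft failure already yields a random and an MMTT C-peptide at the same cut-off, only earlier. The data to count usually exist; the counting convention does not. The pooled run also has a purpose of its own: it responds to causes common to both arms, such as the islet preparation or the shared immunosuppression.

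A reader might also infer that discretionary DSMB review is the only fallback. It is not. Section 10.6 gives a two-sided between-arm boundary on 75-day C-peptide that can conclude LMW-DS is inferior. With SD 0.9 nmol/L, that boundary is crossed against LMW-DS by 24 subjects in about 51%, 74% and 90% of simulated trials for mean shortfalls of 1.0, 1.25 and 1.5 nmol/L. This stands, but section 10.6 presents the schedule as an example, section 10.5 ties interim analyses to a request, and the first look needs |z| above 3.71.

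Nor does the pooling criticism carry over to rule 2. A pooled run of 3 still fires in about 66-99% of these scenarios, ignoring its two-site condition.

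Finally, the within-arm run is itself weak at moderate failure rates: 11% at 50% and 50% at 70%. That is true, and it limits what the change can achieve.

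**Conclusion.** Both weaknesses stand, in limited form. The Day-75 requirement in rule 3 conflicts with the exemption stated beside it and elsewhere, so failures confirmed earlier can go uncounted. How much this costs depends on how many failures skip the visit. The pooled run detects failure common to both arms (96% at an 80% rate, all values present) but has little sensitivity to failure confined to LMW-DS: about 0.6-12% at 80% versus 5-10%, against 77% within the arm. The size rests on assumed failure rates and block sizes; the direction does not. Because other safeguards exist, this is a gap in one trigger, not an absence of monitoring. It should be closed because doing so is cheap.

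**What to change.** Amend section 6.2 in two places.

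1. State that a graft failure confirmed by random and MMTT C-peptide at any time up to Day 75 counts toward the six, with or without a Day-75 assessment. Reconcile this with rule 2, the Study Definitions Page and section 5.15.3, and name the order that defines consecutive subjects.
2. Keep the pooled run of six and add the same run counted within each arm.

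The cut-off and run length stay as they are, and no treatment or visit changes. No new data are needed, and because the trial is open-label the coordinating center can count by arm. The cost is a short amendment and somewhat more holds for review: about 3% of trials instead of about 1.6% at a 30% failure rate in both arms.
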